3.5 Study Duration

This study will consist of a screening period of up to 5 weeks, a 24-week open-label treatment period and a follow up period of up to 16 weeks. The duration of the study is a minimum of 24 to 40 weeks, plus up to 5 weeks for the screening period.

The subject's participation in the study will be considered to have ended at the time of the last visit.

The overall duration of the study will be approximately 32 months, including approximately 21 months' recruitment. The study will be considered to have started when the first subject has been screened. The study will be considered to have ended after the last subject has completed the last visit in the study.

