4.3 Subject Withdrawal Criteria and Procedures

In accordance with the Declaration of Helsinki, each subject is free to withdraw from the study at any time. The investigator also has the right to withdraw a subject from the study in the event of concurrent illness, AEs, pregnancy (see Section 8.1.5), or other reasons concerning the health or wellbeing of the subject, or in the case of lack of cooperation. In addition, a subject may be withdrawn from the study as described in Sections 3.6, 6.2 and 8.1.7.

Should a subject decide to withdraw from the study after administration of the IMP, or should the investigator decide to withdraw the subject, all efforts will be made to complete and report the observations up to the time of withdrawal as thoroughly as possible. A complete final evaluation at the time of the subject's withdrawal should be made (see Section 5.2.4.4) and an explanation given of why the subject is withdrawing or being withdrawn from the study.

The reason for and date of withdrawal from the study must be recorded on the eCRF. If a subject withdraws consent, every attempt will be made to determine the reason. If the reason for withdrawal is an AE or a clinically significant laboratory test abnormality, monitoring will continue until the event has resolved or stabilised, until the subject is referred to the care of a local health care professional, or until a determination of a cause unrelated to the IMP or study procedure is made. The specific AE or test result(s) must be recorded on the eCRF. All evaluations should be performed, according to the protocol, on the last day the subject receives IMP, or as soon as possible thereafter.

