5 STUDY PROCEDURES

5.1 Study Schedule

The schedule of procedures and assessments during the study is summarised in [Table 2](#). Procedures and assessments specific to the PK and PD subgroups are summarised in [Table 3](#) and [Table 4](#).

Table 2 Study Procedures and Assessments (All Subjects)

	Screening period	Treatment period										Follow up period [a]		
	Visit 1	Visit 2	Visit 3	Visit 4	Visit 5	Visit 6	Visit 7	Visit 8	Visit 9	Visit 10	Visit 11	End of study/early withdrawal visit		
Procedures and assessments	Screening up to -5 weeks	Baseline	Week 4	Week 8	Week 12	Week 16	Week 20	Week 24	Week 28	Week 32	Week 36	Within 15 days after menses recovery or Week 40[b]		
Visit window (days)	-35 to -1	Day 1	Day 29 ±3	Day 57 ±3	Day 85 ±3	Day 113 ±3	Day 141 ±3	Day 169 ±3	Day 197 ±3	Day 225 ±3	Day 253 ±3	(Day 281±3 days)		
Prior and concomitant medication/therapies	X	X	X	X	X[j]	X[j]	X[j]	X	X	X	X	X		
Status of menses	X	X	X	X	X	X	X	X	X	X	X	X		

AE=adverse event; E₂=oestradiol; ECG=electrocardiogram; FSH=follicle stimulation hormone; LH=luteinising hormone; PK=pharmacokinetic; VAS=visual analogue scale

- a during the follow up period, the first visit after menses recovery, or Week 40 (whichever is earlier) will be considered the final visit (end of study). The end of study visit should be a clinic visit. Follow up visits prior to the end of study visit will be telephone contact visits
- b or upon early withdrawal from the study
- c samples taken pre-dose, where applicable
- d only if subject's menses do not recover before Week 40
- e subject height and weight will be assessed at screening only
- f samples for clinical laboratory testing will be taken after at least 8 hours fasting
- g a result within 1 month prior to the screening visit will be acceptable
- h optional, based on the subject's disease condition, as judged by the investigator
- i study treatment must be initiated during the subject's follicular phase (first to fifth day of menses period)
- j from Week 12, after the primary endpoint evaluation, "add back" treatment will be permitted if needed according to the investigator's judgement. "Add back" treatment will be recommended as, but not limited to, tibolone 2.5 mg once daily

Table 3 Full PK/PD Assessments Day 1 to Week 12 (PK/PD Subgroup Subjects)

Assessment[a]	Treatment period											
	Day 1	Week 1 (hours post Day 1 dosing)		Week 2	Week 3	Week 4	Week 6	Week 8	Week 10	Week 12		

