5.2.4.4 End of Study Visit or Early Withdrawal Visit

The end of study visit will be the first visit within 15 days after the first day of menses recovery, or at Week 40 (Day 281±3), whichever is earlier. Subjects who withdraw from the study early will also attend an end of study visit.

Subjects who participate in the study in compliance with the protocol for 24 weeks of study drug administration will be considered to have completed study treatment. Subjects who participate in the study in compliance with the protocol for the 24 weeks of study drug administration, and complete the follow up period, will be considered to have completed the study.

For subjects who complete the study, or for those who withdraw prematurely from the study, final evaluations will be performed on the last day the subject receives the study drug, or as soon as possible afterwards. Subjects with ongoing AEs or clinically significant laboratory test abnormalities (as determined by the investigator) will be monitored as described in Section 8.1.3 and Section 8.1.2.4, respectively.

The following procedures will be performed at the end of study visit:

- E₂, LH and FSH concentrations (only if the subject's menses does not recover before Week 40)

- VAS assessment
- Vital signs
- Review of AEs
- New or changed concomitant medications/therapies
- Review of menses recovery status and record the date of menses onset (if applicable)

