6.3 Procedures for Monitoring Subject Compliance

The investigator will be responsible for monitoring subject compliance. Subjects can be withdrawn from the study at any time if the investigator or the sponsor determines that the subject is not in compliance with the study protocol.

For this study, all doses of IMP will be administered to the subjects at the study centre by study site staff. Administration of IMP must occur at the study day indicated ± 3 days. Administration compliance will be assessed by comparing the number of doses expected with the number of doses administered. Any missing injection at Visits 2, 3 or 4 (Day 1, Week 4 or Week 8) will be regarded as a major protocol violation.

Where a subject is consistently noncompliant with IMP intake they should be discontinued from IMP/withdrawn from the study. Please refer to Section 4.3 for the criteria for discontinuing the subject from IMP.

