The severity of endometriosis-associated pain will be assessed by the subject at Day 1 (baseline), Weeks 4, 8, 12, 16, 20, 24, and at the end of study visit using a 10 cm VAS. Subjects will be asked to assess their most severe endometriosis-associated pain over the preceding 4 weeks. For the Day 1 (baseline) assessment, if subjects had undergone endometriotic surgery within the previous 4 weeks, they will be asked to assess their most severe endometriosis-associated pain postsurgery. The VAS to be used is presented in Appendix 1.

7.3.3 *Recovery of Menses*

Status of menses recovery will be assessed at all study visits, including the follow-up period (Weeks 28, 32, 36 and at the end of study visit). The date of menses (if available) will be recorded at the end of study visit. Time to menses recovery will be defined as the time (in days) between the date of the last dose of study drug and the date of the first day that the subject observed menstrual bleeding of the next menses period. Any subjects withdrawing from the study without menstrual bleeding will be censored in this analysis at the date of withdrawal. Any subjects without menstrual bleeding prior to the end of study visit will be censored in this analysis at the date of the end of study visit.

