8.1.5 Pregnancy

Pregnancy itself is not regarded as an AE unless there is a suspicion that the IMP has interfered with a contraceptive method. If pregnancy occurs during the study, the outcome of the pregnancy will then need to be collected poststudy and it may be necessary to discontinue administration of the IMP.

Information regarding pregnancies must be collected on the AE page of the eCRF and reported to the sponsor as an SAE. The sponsor will request further information from the investigator as to the course and outcome of the pregnancy using the Standard Pregnancy Outcome Report Form.

The investigator must instruct all female subjects to inform them immediately should they become pregnant during the study. The investigator should counsel the subject, discuss the risks of continuing with the pregnancy and the possible effects on the foetus. Monitoring of the subject should continue until conclusion of the pregnancy, which may involve follow up after the subject's involvement in the study has ended.

Pregnancies with a conception date within 150 days (for subjects receiving triptorelin pamoate PR 3-month), or 90 days (for subjects receiving triptorelin acetate PR 1-month) after subject's last dose of the study drug must also be reported to the investigator for onward reporting to the sponsor.

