7.7.1 Adverse Events

A treatment-emergent adverse event (TEAE) is defined as any AE that occurs or worsens on or after the first dose of IMP, through 112 days (16 weeks) after last injection for triptorelin pamoate PR 3-month groups or through 56 days (8 weeks) after injection for triptorelin acetate PR 1-month group. Non-TEAEs and TEAEs will be separately summarised in tables and all AEs will be presented in the listing with flag of TEAE status.

All adverse events (AEs) recorded on the eCRF will be coded to SOC and PT using the MedDRA dictionary (version number is the newest version used in Covance coding system at the time of analysis). A subject will be counted at most once within a SOC and PT in summary tables.

In the summary table of TEAEs, the numbers and percentages of subjects and events will be tabulated and presented by treatment groups and overall for the following categories:

- Any TEAEs
- TEAEs with maximum intensity (Severe, Moderate, Mild)
- Serious TEAEs
- Drug-related TEAEs
- Drug-related serious TEAEs
- TEAEs leading to drug withdrawal
- TEAEs leading to drug interruption
- Serious TEAEs leading to drug withdrawal
- Serious TEAEs leading to drug interruption
- TEAEs leading to death

The numbers and percentages of subjects and events will be also be separately summarised by SOC and PT (sorted alphabetically) for each treatment group and overall as the above AE categories. The TEAEs with intensity of Severe will be separately summarised by SOC and PT (sorted alphabetically) for each treatment group and overall. The TEAEs and drug-related TEAEs will be also separately summarised by maximum intensity, SOC and PT (sorted alphabetically) for each treatment group and overall.

TEAEs or drug-related TEAEs with PTs observed $\geq 5\%$ or $\geq 10\%$ of subjects in any one of the treatment groups will be separately summarised by SOC and PTs.

In the event of multiple events being reported by the same subject, the maximum intensity (severe, missing, moderate, mild) and the most serious causality (related, not related) will be chosen. If severity is missing for one event and the subject had no intensity of severe in the same category events, “missing” row should be added after severe in the summary tables with maximum intensity.

Statistical Analysis Plan

Version: Final 3.1

Ipsen Pharma; Protocol No. D-CN-52014-220

Date of Issue: 13DEC2019

CCI

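### No contact is scheduled after an early-withdrawal visit, although the SAP counts treatment-emergent events for 112 or 56 days after the last injection

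*Protocol*

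**What the plan says.** **Timing of the last evaluation.** Protocol 5.2.4.4 states, for completers and premature withdrawals together, that "final evaluations will be performed on the last day the subject receives the study drug, or as soon as possible afterwards". Section 4.3 has the same rule for withdrawals: evaluations take place "on the last day the subject receives IMP, or as soon as possible thereafter". A footnote to Table 2 (section 5.1) places the visit "or upon early withdrawal from the study". Under section 3.5, a subject's "participation in the study will be considered to have ended at the time of the last visit".

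**Telephone follow-up.** Sections 3.1, 5.2.4 and 5.2.4.1 describe calls at Weeks 28, 32 and 36, after 24 weeks of treatment. The calls cover adverse events, concomitant medication and menses status. No equivalent is written for a woman who stops earlier.

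**Stopping drug and leaving the study.** Section 6.3 says of consistently noncompliant women that "they should be discontinued from IMP/withdrawn from the study".

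**Menses recovery.** Protocol 7.3.3 times this secondary endpoint from the last dose and adds: "Any subjects withdrawing from the study without menstrual bleeding will be censored in this analysis at the date of withdrawal". SAP 7.6.2 keeps that rule for withdrawals.

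**TEAE period.** Protocol 10.4.8 ends it at the end-of-study or early-withdrawal visit. SAP 7.7.1 runs it "through 112 days (16 weeks) after last injection for triptorelin pamoate PR 3-month groups or through 56 days (8 weeks) after injection" for the 1-month arm. SAP section 8 records no change from the planned analyses.

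**Safeguards.**
- Ongoing events, and those that caused withdrawal, are followed (protocol 4.3, 5.2.4.4, 8.1.3).
- Suspected-related events after study completion must be reported (8.1.4).
- Section 8.1.5 makes these reportable: "Pregnancies with a conception date within 150 days (for subjects receiving triptorelin pamoate PR 3-month), or 90 days" for the 1-month arm, counted from the last dose.

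**The concern.** The SAP defines a post-injection period of interest, but for early stoppers the protocol provides no scheduled means of collecting events during it. The period is twice as long after a 3-month injection as after a 1-month injection, so the shortfall need not be equal between arms.

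Two stated aims are touched. The safety profile of the 3-month product is a secondary objective. A new event that begins after the withdrawal visit, and that nobody suspects to be drug-related, has no scheduled route into the data. Time to menses recovery is a secondary endpoint, and a woman evaluated on her last dosing day would be censored at about day 0 and contribute almost nothing. Her reason for stopping may also be related to the outcome.

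Separately, the sentence on final evaluations also covers completers. It cannot be squared with the end-of-study visit that the same section sets for them.

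**Working it through.** **1. The plan's own figure, and the dropout number.** Protocol 10.2 gives 133 per arm, for 92% castrated in both arms (equal rates assumed), a margin of 10 points, one-sided 0.025 and 85% power:

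n = (1.960 + 1.036)² × 2 × 0.92 × 0.08 / 0.10² ≈ 132.2, rounded up to 133; power at 133 is 85.2%.

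Allowing for 10% dropout, 133 / 0.9 gives 148 per arm, or 296 in total, consistent with the planned 300. The sample size is not in question. Only the dropout figure is used below: 0.10 × 150 = 15 women per arm, assuming an equal split.

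**2. Inputs.** Scheduled dosing days (protocol 3.1 and Table 2) are Days 1 and 85 in the 3-month arm, and Days 1, 29, 57, 85, 113 and 141 in the 1-month arm. TEAE windows (SAP 7.7.1) are 112 and 56 days.

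Unsolicited window = day of last injection + 112 or 56 − day of leaving.

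**3. Women who receive every dose.** 85 + 112 = Day 197 and 141 + 56 = Day 197. Both windows close on the target day of Visit 9 (Week 28), an existing telephone contact. The SAP window therefore fits the schedule for women still in follow-up then. For early stoppers no scheduled contact covers it.

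**4. Women who stop early.**

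| Leaving day | 3-month arm | 1-month arm | Excess |
|---|---|---|---|
| Day 29, dose due not given (1-month) | 1+112−29 = 84 | 1+56−29 = 28 | 56 |
| Day 29, dose given (1-month) | 84 | 29+56−29 = 56 | 28 |
| Day 43 | 1+112−43 = 70 | 29+56−43 = 42 | 28 |
| Day 71 | 1+112−71 = 42 | 57+56−71 = 42 | 0 |
| Day 85, dose not given (both) | 1+112−85 = 28 | 57+56−85 = 28 | 0 |
| Day 85, dose given (both) | 112 | 56 | 56 |
| Day 113, dose due not given (1-month) | 85+112−113 = 84 | 85+56−113 = 28 | 56 |

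If doses are given as scheduled, the excess is 56 days in the first 4 weeks of each 12-week cycle, 28 days in the next 4 and 0 in the last 4. It is never negative.

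**5. Average, under an assumption.** Suppose the leaving day is uniform over the 24 weeks. The 3-month remainder runs from 112 down to 29 in each cycle, mean (112 + 29)/2 = 70.5 days. The 1-month remainder runs from 56 down to 29, mean (56 + 29)/2 = 42.5 days. The mean excess is 28 days. The 3-month window is longer on two thirds of leaving days and equal on one third.

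**6. Upper bound.** If every withdrawal visit fell on the last dosing day, the unsolicited time would be 15 × 112 = 1,680 person-days against 15 × 56 = 840.

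**7. Passages set side by side.**
- *Completers.* The last dose is at Week 12 (3-month) or Week 20 (1-month). Section 5.2.4.4 sets their end-of-study visit within 15 days of menses recovery or at Week 40, yet also sets final evaluations at or soon after the last dose.
- *TEAE period.* For an early stopper the SAP period outlasts the protocol's. For a completer followed to Week 40 (Day 281) the order reverses: the protocol counts 281 − 197 = 84 days that the SAP does not.
- *AE collection.* Section 8.1.1 runs it to the end of the study under section 3.5, which gives both a subject-level and a study-level end. The cut-off for withdrawn women is therefore unclear.

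**The case against.** The strongest reply is that the protocol already protects what matters most. An event that causes withdrawal is monitored until it resolves, stabilises, is referred or is found unrelated (4.3). Other ongoing events are followed too (8.1.3), and later suspected-related events and pregnancies are reportable. This stands. A reader might infer that adverse events after withdrawal go unobserved, or that women who tolerate treatment badly are simply lost; the documents do not support either. The safeguards do not, however, prompt anyone to ask about new events. They also leave later reporting to a causality judgement made open-label.

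A reader might also infer that the protocol equates stopping drug with leaving the study. The section 6.3 wording concerns consistent noncompliance and can be read as either action. Elsewhere the two are kept apart: section 5.2.4.4 distinguishes completing treatment from completing the study, and section 10.4.3 tabulates discontinuation of treatment. The text is ambiguous, and it schedules nothing for a woman who stops injections but stays reachable.

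The last-dosing-day case (112 versus 56 days) is the extreme one. Table 2 ties the visit to withdrawal itself, and SAP Table 1 re-maps withdrawal visits to windows that include days between doses. That stands, and is why the excess is given by leaving day.

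Finally, menses recovery is summarised by per-arm Kaplan-Meier estimates without a between-arm test, and censoring at withdrawal is the consistent choice when no later data exist. Both are true. The second ceases to apply once calls continue.

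**Conclusion.** The point holds as a gap in scheduled data collection and as a set of passages that must be reconciled. After an early-withdrawal visit nobody is scheduled to ask about new adverse events or menses, although the SAP's TEAE period continues. For the same leaving day that period is longer in the 3-month arm by 56, 28 or 0 days.

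A reader might go further and conclude that adverse events in the 3-month arm are under-ascertained relative to the comparator. That is possible but not shown: it depends on the number and timing of withdrawals and the late-event rate in each arm, none of which the documents give. Nor do they state how long either depot releases drug, so the calculation rests on the SAP windows and makes no claim about release.

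The assumptions are 10% dropout split equally (about 15 women per arm), doses on scheduled days and, for the averages only, a uniform leaving day. The number actually reachable will be smaller, because some women will refuse contact. The Week 12 primary analysis and its sample size are unaffected. This is a worthwhile, inexpensive improvement to safety ascertainment and to one secondary endpoint.

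**What to change.** 1. Record stopping study drug separately from withdrawing from the study.
2. For women who stop study drug and accept contact, keep the existing 4-weekly telephone contact (adverse events, concomitant medication, menses status) until menses recovery or Week 40, and at least to the end of the SAP's 112- or 56-day window.
3. Censor menses recovery at the last known menses status instead of at withdrawal.
4. Align the TEAE definitions in protocol 10.4.8 and SAP 7.7.1, and record the change in SAP section 8. State which end in section 3.5 governs AE collection for women who leave early.
5. Reconcile the sentence in 5.2.4.4 on final evaluations at the last dose with that section's end-of-study visit at menses recovery or Week 40.

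Cost: a short amendment and calls to roughly 30 women, using the contact already defined in 5.2.4.1. Covering only the SAP window takes at most 112/28 = 4 calls per woman in the 3-month arm and 56/28 = 2 in the 1-month arm, so at most 15 × 4 + 15 × 2 = 90 calls. Going on to menses recovery or Week 40 takes more: up to (281 − 29)/28 = 9 contacts for a woman who leaves at Week 4. Some women will decline, so the gap will narrow but not close.

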6 TREATMENT OF SUBJECTS

6.1 Study Drugs Administered

At screening, subjects will be allocated a subject number. Following confirmation of eligibility for the study at baseline (Visit 2, Day 1), subjects will be allocated a randomisation number, and assigned to one of the following treatment groups:

- triptorelin pamoate PR 3-month, administered as an intramuscular injection once every 12 weeks (a total of 2 injections).

or

- triptorelin acetate PR 1-month, administered as an intramuscular injection once every 4 weeks (a total of 6 injections).

6.1.1 *Triptorelin Pamoate PR 3-month*

The test product is triptorelin pamoate PR 3-month, which comprises microparticles with the active ingredient incorporated in the copolymer. The product is presented as a slightly yellow freeze-dried cake or powder containing triptorelin pamoate; D, L-lactide-coglycolide polymer, mannitol, sodium carmellose and polysorbate 80. The solvent provided for injection is a 2 mL ampoule of mannitol and water. This product is marketed in China as Triptorelin pamoate for injection 15 mg, for the treatment of prostate cancer only.

Triptorelin pamoate PR 3-month is to be administered by the intramuscular route only. The powder is reconstituted with the solvent provided and injected immediately after reconstitution. The product is administered as a single intramuscular injection every 12 weeks (Day 1 and Week 12), as indicated in [Table 2](#).

6.1.2 *Triptorelin Acetate PR 1-month*

The comparator product is triptorelin acetate PR 1-month, which is formulated as microparticles. The comparator is presented as a practically white, freeze-dried cake or powder containing triptorelin acetate; D, L-lactide-coglycolide polymer, mannitol, sodium carmellose and polysorbate 80. The solvent provided for injection is a 2 mL ampoule of mannitol and water. This product is marketed in China as Diphereline 3.75 mg for various indications including the treatment of endometriosis.

Triptorelin acetate PR 1-month is to be administered by the intramuscular route only. The powder is reconstituted with the solvent provided and injected immediately after reconstitution. The product is administered as a single intramuscular injection every 4 weeks (Day 1 and Weeks 4, 8, 12, 16 and 20) as indicated in [Table 2](#).

